3.6.4 Laboratory-confirmed co-infection

Laboratory-confirmed co-infection is defined as two or more laboratory-confirmed infections (Section 3.6.3) on any respiratory sample taken in the accepted timeframe (collected between 14 days prior to and up to 72 hours after hospital admission).

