Data collected at Study Contributors will be checked for quality and transferred to a dedicated, secured central server hosted by P95. A data management plan (DMP) will be written prior to the start of the data collection. The DMP will describe all functions, processes, responsibilities and specifications for data collection, cleaning, and validation.

Confidential Version 1.0

Ethical considerations

The protocol will be submitted to relevant ethics committee(s) following local regulations. Informed consent will be obtained from participants/guardians as specified by the national/regional ethics committee.

Study limitations

When using sentinel surveillance, generalisability may be limited as social and demographic factors are usually not uniform across a country and thus the catchment population of a sentinel network may not be comparable with the remaining population of a country. Current active sites cover between 6.8% (Germany) to 16.2% (Belgium) of their countries' population, which is above the World Health Organization (WHO) recommended coverage for sentinel surveillance (at least 1-2% of a population) [1].

Under-detection of pathogens of interest may occur. RT-PCR sensitivity is influenced by several factors, including operator sampling technique, type of respiratory specimen, number of specimens collected, and timing of sampling [2, 3]. Assay sensitivity may also vary across pathogens. To limit under-detection, only assays with high sensitivity are used, sampling is performed in the first 72h after hospital admission, and information on the main factors influencing result RT-PCR are collected. Guidance on collecting and handling specimens for the diagnosis of viral respiratory pathogens are given as part of study staff training.

With RT-PCR, a positive result is highly specific for the presence of the viral pathogen nucleic acid of interest. However, RT-PCR does not differentiate between viable and nonviable virus, and a positive result may indicate an older infection, non-causal to the current SARI episode. Notably, as only results of specimens sampled within 72h after admission are included, inclusion of hospital-acquired infections will be avoided.

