2.2 Secondary objectives

3 To investigate the prevalence of co-infection with the viral respiratory pathogens of interest¹, in adult patients hospitalised with SARI, and the impact on healthcare utilisation outcomes².

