3.6.3 Laboratory-confirmed infection

For each studied pathogen, a laboratory-confirmed infection is a positive reverse transcription polymerase chain reaction (RT-PCR)³ or multiplex RT-PCR on a respiratory specimen(s) collected between 14 days prior to and up to 72 hours after hospital admission. If all samples collected in this time frame are negative, the patient is considered as not having any laboratory-confirmed infection.

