3.8.2 Laboratory testing

To the extent possible, clinical specimens will be collected from the patients eligible for the study as part of routine clinical sampling for diagnostic work-up. However, depending on local practice, additional sampling for the purpose of the study may be required. Samples collected between 14 days prior to and up to 72 hours after admission are accepted. Nasopharyngeal or oropharyngeal swabs are recommended. Additional respiratory specimens are accepted (e.g., nasal swabs, oropharyngeal swab, saliva, mouth wash, bronchoalveolar lavage, aspirates). Sample type will be recorded.

The specimens will be tested within the local laboratory infrastructures of the participating Study Contributors, for at least SARS-CoV-2, influenza A/B and RSV A/B, and preferably also for adenovirus,

Confidential Version 1.0 21 March 2024 Page **28** of **49** Parainfluenza 1-4, human metapneumovirus (hMPV), human rhinovirus (HRV), human enterovirus (HEV), and human coronaviruses (229E/NL63/OC43/HKU1), by using validated RT-PCR or multiplex RT-PCR assays, or another RNA amplification system with at least the same sensitivity as RT-PCR (e.g., transcription-mediated amplification (TMA)). Assays used are either commercial assays with known high sensitivity, specificity and/or concordance, or in-house developed assays that have undergone quality and/or validation processes. Study Contributors will be requested to submit validation logs (summarising the quality check process, results, timing and certificates of analysis for assays performed) to the Study Team.

			Number of pathogens
Study Contributor, Country	Brand	Panel	tested
VAHNSI,	In-house	In-house	20
Spain			
Val d'Hebron,	SeeGene	Allplex RP 1-3	19
Spain	Cepheid GeneExpert	Xpert [®] Xpress CoV-	4
		2/FLU/RSV plus	
GHTiP,	SeeGene	Allplex SARS-CoV-	4
Spain		2/FLU/RSV	19
		Allplex RP 1-3	
Hospital Clínico Universitario de	BioFire	FilmArray	18
Santiago de Compostela,			
Spain			
Hospital Clínic de Barcelona,	GeneXpert	ТВС	
Spain			
Hospital Universitario La Paz,	BioFire	ТВС	
Spain	Cepheid GeneXpert		
CIRI-IT,	SeeGene (Bari, Genoa)	Allplex RP 1-3	19
Italy	In-house (Milan)		
	TBC (Sienna, Pisa)		
Luigi Sacco Hospital,	SeeGene	Allplex RP	21
Italy			
UZA,	Pathofinder	Respifinder 2smart	18
Belgium			
St Pierre,	Qiagen Qiastat	RP SARS-CoV-2	18
Belgium	Abbott Alinity m RESP		4
	4-plex TaqMan	In-house	17
Universitäts-klinikum Frankfurt,	SeeGene	Allplex RP 1-3	19
Germany	BioFire	FilmArray RP2.1	18

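### Co-infection is counted on any number and type of specimen, so if early-severe patients are sampled more, the objective 3 comparison with severity can show an association that is only differential detection

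*Protocol*

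**What the plan says.** Section 3.6.4 defines the exposure: "Laboratory-confirmed co-infection is defined as two or more laboratory-confirmed infections (Section 3.6.3) on any respiratory sample taken in the accepted timeframe", that is, samples "collected between 14 days prior to and up to 72 hours after hospital admission". This is a window of 14 days plus 72 hours, or 17 days.

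Section 3.6.3 gives the rule for the opposite status: "If all samples collected in this time frame are negative, the patient is considered as not having any laboratory-confirmed infection". An additional specimen can therefore add a detected pathogen but never remove one.

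Section 3.8.2 says that, as far as possible, specimens are collected "as part of routine clinical sampling for diagnostic work-up". It recommends nasopharyngeal or oropharyngeal swabs and continues: "Additional respiratory specimens are accepted (e.g., nasal swabs, oropharyngeal swab, saliva, mouth wash, bronchoalveolar lavage, aspirates). Sample type will be recorded". Extra sampling for the study is allowed where local practice requires it.

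The study limitations in the abstract acknowledge that "RT-PCR sensitivity is influenced by several factors, including operator sampling technique, type of respiratory specimen, number of specimens collected, and timing of sampling". Section 5 has a similar list but treats the matter only as under-detection. Section 3.13.5 plans a correction for single-specimen sensitivity, for incidence rates only.

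The secondary objective in section 2.2 covers the prevalence of co-infection "and the impact on healthcare utilisation outcomes". Section 3.13.2 describes co-infection percentages by those outcomes. Section 3.6.5.1 classifies severity by the worst level reached during the stay.

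**The concern.** For a prevalence figure, an any-positive rule over all specimens is a reasonable choice. For a comparison by severity it is fragile, because the chance of being classified as co-infected rises with the number of specimens and changes with their type. Both are left largely to clinical practice.

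A patient who needs ICU care or intubation within 72 hours of admission may well have a repeat swab, an aspirate or a lavage that a stable ward patient does not have. Co-infection would then be found more often in severe patients even if the true frequency were the same. The result could be read as co-infection worsening the course of SARI, which is how the objective is worded. The mechanism is differential detection, that is, misclassification of the exposure that depends on the outcome.

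**Working it through.** **The plan's own figures.** The protocol gives no figure for co-infection or for objective 3. Its analysed sample size reproduces: 300 × 22 = 6,600, and 6,600 × 0.9 = 5,940. Table 1 sums to 22 hospitals. The six precision values in Table 4 also reproduce as half-widths of exact 95% intervals at 5,940. I use N = 5,940 below.

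**Assumed inputs (none is in the documents).**
- True co-infection prevalence c, equal in severe and other patients (no true effect): 5%.
- Sensitivity s per virus and per specimen: 0.7 to 0.95.
- Share of severe patients: 10% or 20%.
- Share of patients with a second specimen: varied below.
- Specimens, and the two viruses, are detected independently.

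**Formulas.** With one specimen, both viruses are found with probability s². With two specimens, each virus is found with probability 1 − (1 − s)² = s(2 − s), so both are found with probability s²(2 − s)². If all severe patients have two specimens and all others one, the risk ratio (RR) is (2 − s)², whatever c is.

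If a fraction f of severe and g of other patients have a second specimen:

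RR = [f·s²(2 − s)² + (1 − f)·s²] / [g·s²(2 − s)² + (1 − g)·s²]

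**Example at s = 0.8.** One specimen: 0.64. Two specimens: 0.96² = 0.9216.
- Extreme contrast (f = 1, g = 0): observed co-infection 0.05 × 0.9216 = 4.6% against 0.05 × 0.64 = 3.2%. RR is 1.44 and the odds ratio (OR) 1.46.
- Milder contrast (f = 0.5, g = 0.1): (0.4608 + 0.32) / (0.09216 + 0.576) = 0.7808 / 0.6682 = 1.17.

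| s | RR, extreme | OR, extreme | RR, 50% vs 10% |
|---|---|---|---|
| 0.70 | 1.69 | 1.72 | 1.26 |
| 0.80 | 1.44 | 1.46 | 1.17 |
| 0.90 | 1.21 | 1.22 | 1.08 |
| 0.95 | 1.10 | 1.11 | 1.04 |

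**Chance of a nominally significant false association** (N = 5,940, c = 5%, two-sided 5% test; severe share 10% to 20%):
- Extreme contrast: 65% to 85% at s = 0.7, 45% to 64% at s = 0.8, 18% to 27% at s = 0.9.
- Milder contrast: 18% to 26% at s = 0.7, 12% to 17% at s = 0.8, 6% to 8% at s = 0.9.

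**If both viruses must be in the same specimen.** The wording of section 3.6.4 could be read this way. Two specimens then succeed with probability 1 − (1 − s²)². At c = 5% the extreme-case OR is 1.53, 1.38 and 1.20 at s = 0.7, 0.8 and 0.9. The effect shrinks but stays.

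**With one specimen of the same type per patient,** observed co-infection is c·s² in both groups and the RR is 1.00.

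**The case against.** The strongest objection is that no passage says sampling differs by severity. The abstract has specimens taken from all included patients, with a nasopharyngeal swab preferred. This stands: the premise is an inference from routine-care sampling, so the bias is possible, not shown.

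Timing also limits it. Severity is the worst level over the whole stay, but specimens count only up to 72 hours after admission. Later deterioration cannot add qualifying specimens, and the hospital course cannot drive swabs taken before admission. Only patients who are severe early are affected, which is why the extreme contrast is an upper case. Positive correlation between specimens from one patient would lower the figures further, and the protocol says only high-sensitivity assays are used.

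A reader might infer that the named regression factors (age, gender, chronic conditions, smoking) show the problem will go unadjusted. The documents do not support that. Section 3.13.4 gives an open list and fixes no model with co-infection as the exposure. Sample type is recorded, and adjustment or restriction remains open to the SAP. What stands is that the exposure definition is fixed in the protocol and would carry over.

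A reader might also infer that the 17-day window merges two successive infections into one co-infection. That is possible under one reading of section 3.6.4. However, the 14-day look-back matches the symptom-onset window of the SARI definition, so the point is too weak to carry weight.

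**Conclusion.** The concern holds as a conditional one. The definition, the reliance on routine sampling and the stated dependence of sensitivity on specimen type and number together leave the objective 3 severity comparison open to differential detection. The 72-hour limit reduces this but does not remove it, because early ICU admission or intubation can fall within it.

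Under no true effect, a moderate sampling contrast gives RR of about 1.08 to 1.26. The extreme contrast gives OR of 1.22 to 1.72. Both ranges are for per-specimen sensitivity from 0.9 down to 0.7. The sensitivities, the prevalence, the severe share and the re-sampling shares are all assumptions, as is independence of specimens. Higher yield from the lower airway is not modelled.

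Two stronger readings are tempting. One is that the comparison is biased away from the null as a matter of fact; without data on sampling by severity, the most that can be said is that it can be. The other is reverse causation: severity would change whether co-infection is detected, not whether it is present.

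**What to change.** Keep the any-specimen definition for descriptive prevalence. For the objective 3 severity comparison, pre-specify a second analysis on one index specimen per patient:
- Use the first respiratory specimen at admission and require both viruses in that specimen.
- Account for specimen type by stratification or adjustment, not by restriction to the upper airway. Restriction would drop patients with only lower-airway specimens, who may be among the sickest.
- State in advance how patients with only a pre-admission specimen are handled.
- Report the result beside the any-specimen result.

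Tabulate the number and type of specimens by severity level, so that readers can judge whether the premise holds. Describe the finding as an association unless the two analyses agree. Agreement would answer this objection only, not other reasons for caution about a causal reading.

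The cost is protocol and SAP wording, a little more analysis work, and fewer co-infection events in the index-specimen analysis. Sampling date, test result and sample type are already to be collected. The number of specimens is not listed in Table 3 but can be counted if each specimen in the window is entered separately, which should be confirmed.

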3.6.5 Healthcare utilisation outcomes

3.6.5.1 Level of severity

Severity will be assessed in 2 ways, first by ICU admission and in-hospital death outcomes, and through outcomes related to respiratory support.

ICU and in-hospital mortality:

The following three mutually exclusive categories will characterise the worst level of severity of hospitalisation due to SARI:

- 1. Hospital admission without ICU admission and without in-hospital death;
- 2. ICU admission without in-hospital death;

³ Or another RNA amplification system with at least the same sensitivity as RT-PCR (e.g., transcription-mediated amplification (TMA)).

Confidential Version 1.0 21 March 2024 Page **26** of **49**

- 3. In-hospital death
 - a. during ICU stay
 - b. outside of ICU stay

Respiratory support:

The following categories will complement the characterisation of the severity of hospitalisation due to SARI. For each patient, the highest level of respiratory support ever received during the hospital stay will be reported.

- 1. No respiratory support;
- 2. Oxygen therapy (e.g., nasal cannula, mask);
- 3. Non-invasive ventilation (ventilatory support without tracheal intubation; e.g., high-flow nasal oxygen, Continuous Positive Airway Pressure (CPAP) or Bi-level Intermittent Positive Airway Pressure (BiPAP));
- 4. Invasive mechanical ventilation (ventilatory support with tracheal intubation);
- 5. Extracorporeal membrane oxygenation (ECMO).

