Time between symp	tom	Days, continuous
onset and hospitalis	ation	
Long-term care facili	ty	Binary, if no, specification of residential situation before
residence [§]		hospitalisation: Home, Home with nursing care, Transfer from
		another hospital, Rehabilitation centre, Nursing home, other,
		no information
Respiratory support		None, oxygen therapy, non-invasive ventilation, mechanical
		ventilation, extra corporeal membrane oxygenation (ECMO),
		other
Cumulative number	of days of	Days, continuous
non-invasive ventila	tion,	
invasive ventilation,	or ECMO	
Length of hospital st	ау	Days, continuous
Admission to ICU		Binary
Length of ICU stay		Days, continuous
In-hospital death		Binary

Covariate	Description
Post-discharge destination	Home, Home with nursing care, Transfer to another hospital,
	Rehabilitation centre, Nursing home or other long-term care
	facility, Other
Treatments received during	Antibiotics, Antiviral drug(s), Corticosteroid(s), Immune-
hospital stay for the	modulator(s), Anti-SARS-CoV-2 antibodies, Other monoclonal
management of SARI episode	antibodies, None of the above.
	Brand name if anti-SARS-CoV-2 antibodies received during
	hospital stay
Treatments received prior to	Antibiotics, Antiviral drug(s), Corticosteroid(s), Immune-
hospital admission for the	modulator(s), Anti-SARS-CoV-2 antibodies, Other monoclonal
management of current SARI	antibodies, None of the above.
episode	Brand name if anti-SARS-CoV-2 antibodies received during
	hospital stay
Medicinal product for the	Binary. If yes, type (Antiviral drug,
prevention of SARS-CoV-2	Anti-SARS-CoV-2 antibodies, Other), brand and date
(pre- or post-exposure	(month/year) if SARS-CoV-2 monoclonal antibody
prophylaxis) in the 12 months	
prior to current	
hospitalisation	
Medicinal products for the	Binary. If yes, type (Antiviral drug,
prevention of RSV infection	Anti-RSV antibodies, Other), brand and date (month/year) if
within 12 months prior to	RSV monoclonal antibody
current hospitalisation	

*Definitions for each chronic conditions are specified in the id.DRIVE Common dataset case report form

§ At VAHNSI, long-term care facility residents are excluded

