3.13.4 Healthcare utilisation outcomes

Multinomial logistic regression will be used to explore risk factors of pathogen-specific SARI hospitalisation, healthcare utilisation outcomes (as defined in Section 3.6.5), and the presence of co-infections (by number of co-infections and involved pathogens, when feasible). Potential risk factors include age, gender, chronic conditions, smoking). Stratified analyses will be performed by age groups, by gender, by presence of chronic condition and specifically by those with pre-existing immunodeficiency disorders.

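### Respiratory support is scored as SARI severity with no reference to support used before admission, so unchanged home oxygen or CPAP can count as severity

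*Protocol*

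**What the plan says.** Protocol section 3.6.5.1 (Level of severity) describes two scales. The first is ICU admission and in-hospital death. The second is respiratory support, introduced with "The following categories will complement the characterisation of the severity of hospitalisation due to SARI" and scored by the rule "For each patient, the highest level of respiratory support ever received during the hospital stay will be reported". Its level 2 begins "Oxygen therapy (e.g., nasal cannula, mask", and its level 3, non-invasive ventilation, gives as examples "high-flow nasal oxygen, Continuous Positive Airway Pressure (CPAP) or Bi-level Intermittent Positive Airway Pressure (BiPAP". No level is tied to the patient's usual support.

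Table 3 in section 3.9 has one respiratory-support variable, whose coding begins "None, oxygen therapy, non-invasive ventilation, mechanical", and a count of cumulative days of non-invasive ventilation, invasive ventilation or ECMO. Its item on treatment before admission is confined to "management of current SARI" and lists drugs and antibodies only. The abstract's covariate list also has no item for home support. Table 3 is described as a summary of a common case report form that is not part of the protocol.

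Section 3.3.2 defines no exclusions. Section 3.13.4 states: "Multinomial logistic regression will be used to explore risk factors of pathogen-specific SARI hospitalisation, healthcare utilisation outcomes". It refers to section 3.6.5 for those outcomes, names chronic conditions among the potential risk factors, and stratifies by their presence.

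**The concern.** A patient on long-term home oxygen who continues it unchanged in hospital meets level 2. A patient who brings a home CPAP device meets level 3, and each night of use can add to the cumulative days of non-invasive ventilation. In neither case has the infection raised the need for support, yet the scale is presented as severity due to SARI.

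The error would not be spread evenly. Home support is plausibly more common with chronic lung disease and obesity, both listed in Table 3 as chronic conditions. In section 3.13.4 the condition is the predictor and can also raise the recorded outcome by itself, so adjusting for that condition does not remove the effect from its coefficient. Severity comparisons by pathogen (objective 2) or by co-infection (objective 3) can shift as well if the groups differ in chronic disease.

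**Working it through.** The protocol gives no figure on this point to reproduce, so the check is first of the text and then of scale.

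**Text.**
1. Scoring rule (3.6.5.1): highest level ever received during the stay, with no condition that it be new or increased.
2. Interpretation (3.6.5.1): severity of the SARI hospitalisation.
3. Data to separate usual from new support (Table 3, abstract): none listed. COPD with GOLD stage is collected, but does not show whether the patient uses home support.
4. Removal of chronic users (3.3.2): none.
5. Mention among the limitations (section 5): none.
6. Contrast within Table 3: residence before hospitalisation is recorded, which gives discharge destination a baseline. Respiratory support has no counterpart.

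**Illustration of bias.** All prevalences here are assumed; the documents give none. Let *h* be the share of a group using home CPAP or NIV, all of whom continue it in hospital and are recorded as NIV. Let 10% be the true share needing new NIV, equal in both groups. The observed share at level 3 or above is *h* + (1 − *h*) × 0.10.

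| Group | *h* | Observed share | Odds | Odds ratio vs reference |
|---|---|---|---|---|
| Without the condition (reference) | 1% | 0.01 + 0.99 × 0.10 = 10.9% | 0.109/0.891 = 0.1223 | 1 |
| With the condition | 5% | 0.05 + 0.95 × 0.10 = 14.5% | 0.145/0.855 = 0.1696 | 1.39 |
| With the condition | 10% | 0.10 + 0.90 × 0.10 = 19.0% | 0.190/0.810 = 0.2346 | 1.92 |
| With the condition | 15% | 0.15 + 0.85 × 0.10 = 23.5% | 0.235/0.765 = 0.3072 | 2.51 |

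The true odds ratio is 1.0 in every row. The table splits the scale at level 3, whereas the protocol plans multinomial models, so it shows direction and rough size only.

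**Number of patients.** Section 3.10 expects about 5,940 analysable patients. If 3% to 8% (assumed) use home oxygen or NIV, that is 0.03 × 5,940 = 178 to 0.08 × 5,940 = 475. This is an upper bound on the number over-scored, because home users who truly need a higher level are scored correctly. If, as in the table, 10% of them needed the recorded level anyway, the range falls to 0.9 × 178 = 160 to 0.9 × 475 = 428.

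**The case against.** Section 3.6.5 is headed as healthcare utilisation, and the highest support received in hospital is a coherent utilisation measure whatever the patient used before. The regression is exploratory. Chronic conditions are candidate factors and also strata, and COPD stage and asthma severity are collected, all of which can reduce case-mix distortion between pathogens. Further sensitivity analyses may be set in the SAP. No passage contradicts another.

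Most of this stands, and it is why the present outcome should be kept. It does not meet the point in full. Section 3.6.5.1 itself calls the scale a level of severity due to SARI; stratification does not repair the coefficient of the chronic condition; and a SAP analysis cannot use a baseline that was not collected.

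Three stronger readings may tempt a reader, and the documents do not support them:
- *That the study never records home support.* Only its absence from Table 3 and the abstract can be verified, because the full case report form is not shown. If that form has the item, the rule in 3.6.5.1 still makes no use of it.
- *That 178–475 patients will be misclassified.* The percentages are assumed, and the count is an upper bound even on those assumptions.
- *That new or escalated support should replace the outcome.* With a categorical baseline, a home-oxygen user whose flow is raised stays at the same level, so a level-change outcome would under-score the same chronic patients and could reverse the bias.

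**Conclusion.** The point holds as a measurement weakness in one of the two severity scales. As written, section 3.6.5.1 scores unchanged home support as SARI severity, and no variable listed in the protocol allows this to be separated out. Coefficients for chronic conditions, and severity comparisons between pathogens with different case mix, can be biased on this scale and in the cumulative days of non-invasive ventilation. Pathogen proportions and the ICU/death scale are not affected.

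The direction rests on one assumption the documents do not test: that home support is more common in patients with the modelled conditions and is continued in hospital. The size cannot be determined from the documents; the odds ratios of about 1.4 to 2.5 illustrate the assumed range and are not estimates. This is a cheap improvement, not a flaw in the primary objectives.

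**What to change.** 1. Confirm whether the common case report form already records usual respiratory support before the episode. If not, add one item to it and to Table 3: none / oxygen / CPAP or NIV / home ventilation.
2. Keep the highest level ever received as the utilisation measure.
3. For the severity and risk-factor analyses, prespecify an additional analysis that either excludes chronic home-support users or reports the level above the pre-admission level. Present it beside the main result, not in its place.
4. Tabulate cumulative days of non-invasive ventilation separately for home users.

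The cost is one extra item to abstract. Section 3.11 says all data except laboratory results come from existing medical files, so no new data source should be needed. The item may be missing from some charts. Escalation within a level will not be captured, so the level-change version can under-score home users; excluding them limits that analysis to patients without home support. These limits should be stated with the results.
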